Due to the intrinsic variability of cognitive functions in DLB or PDD, subjects who screen fail at Tier 2 may be rescreened after at least 30 days, but as a guide, rescreening frequency should not be more frequent than once every 3 months and a subject should not be rescreened more than 2 times under the same version of the eligibility criteria. For subjects who screen fail at Tier 3 or 4 due to their subgroup already having achieved the target number of subjects, they may be rescreened if a new subject is required in their subgroup due to early discontinuation. If this rescreening occurs within 30 days after screen fail, the history of DLB or PDD in Tier 1 and the assessments at Tiers 2, 3, and 4 do not need to be repeated unless clinically indicated in the investigator's judgement.

All subjects who have completed screening assessments in Tiers 1 to 6 and are deemed eligible for the study will have a baseline CSF sample collected by lumbar puncture (LP). The CSF sample will be collected in the morning, either in the fasted state or at least 2 hours after breakfast. In subjects who require DAT or MIBG scan, the CSF collection should be at least 1 week after the scan.

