9.5.1.3.1 PHARMACOKINETIC ASSESSMENTS

Blood samples will be collected for the determination of plasma E2027 concentrations for PK analysis. Two blood samples for PK will be drawn at Weeks 6, 9, and 12: At predose (within 30 minutes before dosing) and 1 to 4 hours postdose. At these visits, subjects or their caregivers or informants will be instructed not to take their study drug at home on the day the blood samples for PK are collected. Instead, subjects will take their study drug at the clinic

after the predose blood draw; then a postdose blood draw will be performed. In addition, subjects or their caregivers or informant will be instructed to record the time of study drug administration for the 2 days before these visits when self-administered at home and this information will be collected and recorded on the eCRFs.

CSF samples will be collected for the determination of CSF E2027 concentrations at Week 9. At this visit, a predose blood sample for PK will be taken first, followed by CSF sampling. Study drug will then be administered to the subjects. Another PK sample will be collected at 1 to 4 hours postdose.

Plasma concentrations of E2027 and its metabolite HP4 and CSF concentrations of E2027 will be measured using validated liquid chromatography with tandem mass spectrometry (LC-MS/MS) assay methods.

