9.5.1.3.2 PHARMACODYNAMIC, PHARMACOGENOMIC, AND OTHER BIOMARKER, ASSESSMENTS

Baseline Biomarker Assessments

A plasma sample will be collected during the Screening Period (Tier 3) to measure biomarkers related to AD copathology (including amyloid and p-tau) and other biomarkers related to DLB or PDD. These baseline plasma amyloid A β 42/A β 40 ratio will be used to classify subjects into the various categories (DLB without amyloid copathology, DLB with amyloid copathology, PDD without amyloid copathology and PDD with amyloid copathology). The baseline plasma biomarkers may also be used to define other subgroups classifications of subjects for subgroup analyses.

A CSF sample will be collected during the Screening Period (at least 7 days before the Baseline Visit) to measure baseline CSF cGMP and biomarkers related to DLB or PDD. These DLB or PDD related biomarkers may be used to define other subgroups classifications of subjects for subgroup analyses.

Plasma concentrations of A β 42 and A β 40 will be measured by the validated immunoprecipitation LC-MS/MS C2N Preclivity plasma assay. Plasma concentrations of p-tau 181, glial fibrillary acidic protein (GFAP), and neurofilament light (NFL) will be measured by Quanterix Simoa plasma assay.

CSF concentrations of cGMP will be measured using a validated assay. Other CSF biomarkers represented by A β 42, A β 40, tau, p-tau will be measured by Lumipulse platform and CSF NFL, neuregulin (NRG) will be measured by Simoa.

Pharmacodynamic Assessments

CSF samples will be collected during the Screening Period (at least 7 days before the Baseline Visit) and after 9 weeks on E2027. Both samples should be collected at approximately the same time in the morning, either in the fasted state (preferred) or at least 2 hours after breakfast. The CSF sample during the Treatment Period should be collected after the predose blood draw for PK and plasma biomarker analysis at the study visit after

9 weeks on E2027. The CSF samples will be assayed for cGMP and E2027. Other CSF biomarkers related to DLB or PDD or E2027 PD effects may also be assayed, if appropriate. CSF concentrations of cGMP and other biomarkers will be measured using validated assays.

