- n: DAT brain imaging scan or myocardial MIBG scan will be performed by the local hospital radiology department in accordance with local procedures and must be performed at least 7 days before CSF collection. The rules regarding when DAT brain imaging or MIBG scan will be performed are specified in Inclusion Criterion 2.
- o: CSF will be collected by LP in all subjects. During Screening CSF may be collected at any time after completion of screening procedures and a subject is deemed eligible, at least 1 week after DAT or MIBG imaging and at least 1 week before Visit 2. CSF will be collected again at Visit 6. CSF will be collected in the morning at approximately the same time, either fasted (preferred) or at least 2 h after breakfast. The timing of the Screening CSF collection needs to be scheduled carefully such that subsequent collection (at Visit 6) can be performed at a similar time of day (± 2 hours) for each individual subject. A gravity drip collection method must be used. Subjects will be encouraged to stay at the site after completion of LP for medical observation as per local guidelines. At Week 9 (Visit 6), a predose blood sample for PK and a blood sample for plasma biomarkers will be taken first, followed by LP. Subjects will then be dosed with study drug and a PK sample will be collected at 1 – 4 hours postdose. If Visit 6 occurs after an ED Visit, blood PK samples, plasma biomarker sample and CSF will not be collected.
- p: The day before the visits at which PK sampling will be done, the site study team will phone the subject and caregiver/informant to remind the subject not to take the study drug in the morning of the visit on the next day. In the morning of the day of the visit, the subjects should take breakfast at home as normal, if applicable. Thereafter, a predose PK sample will be taken in clinic. Study drug will be administered and 1 postdose PK sample will be taken: 1 - 4 hours postdose at Week 6 (Visit 5) and Week 12 (Visit 7) (or ED Visit). At Week 6 (Visit 5) and Week 12 (Visit 7) (or ED Visit) study drug will be administered before efficacy assessments are performed. A predose PK sample and a blood sample for plasma biomarkers will be collected at Week 9 (Visit 6), followed by CSF collection. The subject will then be dosed with study drug and a

Table 5 Schedule of Procedures/Assessments in Study E2027-A001-203

Phase	Pretreatment		Treatment							

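### The breakfast and CSF-sampling instructions are not reconciled for Week 9, and the paired CSF samples are matched on time of day but not on prandial state

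*Protocol*

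**What the plan says.** **Breakfast.** Protocol Table 5 footnote p opens with "The day before the visits at which PK sampling will be done", so it covers every PK visit. Its breakfast sentence reads "In the morning of the day of the visit, the subjects should take breakfast at home as normal, if applicable". Protocol 9.5.1.3.1 lists the PK visits: "Two blood samples for PK will be drawn at Weeks 6, 9, and 12". Footnote p also describes the Week 9 visit itself: "A predose PK sample and a blood sample for plasma biomarkers will be collected at Week 9 (Visit 6), followed by CSF collection". The breakfast sentence makes no exception for that visit.

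**CSF.** Footnote o says "CSF will be collected in the morning at approximately the same time, either fasted (preferred) or at least 2 h after breakfast". Protocol 9.5.1.3.2 repeats the preference for the two samples: "either in the fasted state (preferred) or at least 2 hours after breakfast". Protocol 9.1.1.1, on the Screening sample, lists the two states without a preference: "The CSF sample will be collected in the morning, either in the fasted state or at least 2 hours after breakfast". Protocol 9.1.2.1 does the same for Week 9.

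**Matching and analysis.** Footnote o asks that the Visit 6 collection fall within 2 hours either way of the Screening clock time. Neither document asks for the same prandial state at both collections. The primary endpoint is the percentage change between these two samples (Protocol 9.7.1.1.1). SAP 5.3.2 and 5.5.2 adjust for the baseline value only.

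**The concern.** Screening has no plasma PK draw (Protocol Table 6), so footnote p does not reach the baseline lumbar puncture. There, footnote o's preference for fasting stands alone. At Week 9 the same preference sits beside a general instruction to eat breakfast. A site that applies each footnote where it falls can collect a fasted sample at baseline and a fed one at Week 9, and be fully compliant.

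The protocol evidently thinks prandial state worth controlling, since it states a preference and a minimum interval after eating. Yet it controls clock time within subject and leaves the state free.

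The study is single-arm. If food affects CSF cGMP, a consistent change of state between the two samples would be counted as drug effect in each subgroup's mean change. A change of state in some subjects but not others would add noise, or would bias the subgroup comparison if it fell unevenly, with six completers planned per subgroup.

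**Working it through.** **Step 1. Is a mismatch compliant?**

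| Item | Screening CSF | Week 9 CSF (Visit 6) |
|---|---|---|
| Footnote o / 9.5.1.3.2 | fasted preferred, or 2 h or more after breakfast | the same |
| Footnote p breakfast sentence | does not apply (no plasma PK draw) | applies, qualified by its last two words |
| Time of day | reference | within 2 h of Screening |
| Same state as the other sample | – | not required |

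A fasted sample at 8:00 at Screening and a fed one at 10:00 at Week 9 meet every line. The time window does not prevent the mismatch.

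**Step 2. Reproduce the plan's own figures.** Inputs from Protocol 9.7.2 and SAP 4 are an SD of 60 points and 6 completers per subgroup.

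- SE of a subgroup difference = 60 × √(2/6) = 34.6 points.
- P(observed difference ≥ 30) = 1 − Φ((30 − true)/34.6) = 97.8%, 80.7% and 28.2% for true differences of 100, 60 and 10. All three agree with the plan, so 34.6 is the plan's working scale.

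**Step 3. Assume a food effect.** The documents give none. Take, for illustration only, a 5% to 10% shift in the Week 9 value from the change of state. The direction is unknown.

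*Systematic mismatch, mean change within one subgroup.* A 170% rise means Week 9 is 2.70 times baseline.
- 5%: 2.70 × 1.05 − 1 = 183.5%, a shift of 13.5 points.
- 10%: 2.70 × 1.10 − 1 = 197%, a shift of 27 points.
- If the shift is downward, the readings are 156.5% and 143%.

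*Systematic mismatch, difference between subgroups.* Compare rises of 170% and 200%, a true difference of 30 points.
- 5%: 3.00 × 0.05 − 2.70 × 0.05 = 15 − 13.5 = 1.5 points.
- 10%: 30 − 27 = 3 points.

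Most of the shift cancels because it applies to both subgroups.

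*Unbalanced mismatch.* Each extra mismatched subject in one subgroup of six moves the difference by one sixth of the shift.
- 13.5/6 = 2.25 points; 27/6 = 4.5 points.
- Against an SE of 34.6, this is about 0.06 to 0.13 of a standard error per subject.

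*Added noise.* If half the subjects are mismatched at random, the added SD is half the shift, 6.75 to 13.5 points.
- √(60² + 6.75²) = 60.4; √(60² + 13.5²) = 61.5.
- The SD rises from 60 to at most about 61.5.

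**The case against.** The strongest reply is that the two footnotes can be followed together. Breakfast at home and a lumbar puncture at least 2 hours later satisfies both. The breakfast sentence is qualified, and a site planning a fasted puncture can treat it as not applicable. Footnote o is the CSF-specific rule and names Visit 6. This stands: a reader might infer a contradiction, but the text shows only two instructions that nobody has reconciled. Nor is a fasted Screening sample assured, because Protocol 9.1.1.1 lists both states neutrally. Fasted then fed is a permitted pairing, not a demonstrated tendency.

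A second reply concerns size. A reader might set the 13.5 to 27 point shift beside the 30-point difference of interest and conclude that food could mimic it. The documents do not support that. The 30 points in Protocol 9.2 and 9.7.2 are a difference between subgroups. Protocol 9.2 makes that the main comparison, and the footnotes apply alike to all four subgroups. On the same assumption the contrast moves by about 1.5 to 3 points. A shift of this size would also not put in doubt that cGMP rises, given the 168% mean rise in Study 201 and the approximately 200% seen in Phase 1.

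Third, conditions are partly controlled already: both samples are taken in the morning, clock time is matched, and a fed sample must be at least 2 hours after eating. Protocol 9.5.1.3 leaves collection and handling to a central laboratory manual that is not among the documents. That manual or the eCRF may record the state, so one cannot say that it goes unrecorded.

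What survives is that nothing in the protocol or SAP requires matching or adjusts for a mismatch, and that the breakfast sentence as written can steer Week 9 away from the stated preference.

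**Conclusion.** The gap is real and minor. Footnotes o and p are not reconciled for Visit 6, and the paired samples behind the primary endpoint are matched on time of day but not on prandial state.

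The size depends wholly on an assumed food effect. At 5% to 10%, each subgroup's mean percentage change could be off by about 13.5 to 27 points at a 170% rise if the mismatch were systematic. That matters mainly for describing how large the response is. For example, Protocol 9.2 distinguishes subjects below 170% from those at 190% to 200%. The between-subgroup comparison would move by about 1.5 to 3 points, or by about 2 to 4.5 points for each extra mismatched subject in six, against a standard error of about 35. If food has no effect on CSF cGMP, there is no bias at all. The documents do not show that a bias exists, or its direction.

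**What to change.** 1. In footnote p, have the breakfast sentence defer to footnote o at Visit 6.
2. In footnote o and Protocol 9.5.1.3.2, state that the Week 9 CSF is collected in the same prandial state as that subject's Screening CSF.
3. Record the state at both collections, if the eCRF or laboratory manual does not already capture it.
4. Add the required state to the reminder call that footnote p already schedules for the day before the visit.

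The cost is a few sentences and at most one eCRF item, and some subjects will attend Visit 6 fasted. Protocol 9.4.5 allows E2027 with or without food, so the change does not touch the dosing instructions.

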9.5.2.2 Description of Procedures/Assessments Schedule

Please refer to Table 5 for the timings of the procedures and assessments to be performed during the study. See Sections 9.1 and 9.5 for a full description of the procedures and assessments, respectively, to be performed during this study.

Table 6 presents the number of blood and CSF samples, and the estimated total volume of blood and CSF that will be collected throughout the study. Additional samples may be taken at the discretion of the investigator if the results of any tests fall outside reference ranges or if clinical symptoms necessitate testing to ensure subject safety. Actual specimen volumes may vary based on local regulations.

Table 6 Summary of Estimated Blood and CSF Sample Volumes

Assessment	Total Number of Collection Time Points	Number of Time Points × Volume per Collection (mL)			Total Volume (mL)
		Screening Visit	Baseline Visit (predose)	Treatment and Follow-Up Periods	
Blood					
Chemistry	4	1 × 2.5	1 × 2.5	2 × 2.5	10.0
Vitamin B12	1	1 × 1.3	None	None	1.3
TSH, T4, T3, β -hCG	1	1 × 2.5	None	None	2.5
Hematology	4	1 × 2.0	1 × 2.0	2 × 2.0	8.0
INR, prothrombin time, PTT	1	1 × 2.0	None	None	2.0
PD (biomarkers)	2	1 × 6.0	None	1 × 6.0	12.0
PK	6	None	None	6 × 6.0	36.0
PGx	1	None	1 × 6.0	None	6.0
Total blood volume to be collected		16.3	10.5	51.0	77.8
CSF					
PK and PD	2	1 × 7.0	None	1 × 7.0	14.0
Total CSF volume to be collected		7.0	None	7.0	14.0

β -hCG = beta-human chorionic gonadotropin, CSF = cerebrospinal fluid, INR = international normalized ratio, PD = pharmacodynamic, PGx = pharmacogenomics, PK = pharmacokinetic(s), PTT = partial thromboplastin time, TSH = thyroid stimulating hormone, T3 = triiodothyronine, T4 = thyroxine.

Note: Actual volumes may be less, based on regional differences in Central Laboratories.

9.5.3 Appropriateness of Measurements

All clinical assessments are standard measurements commonly used in studies of LBD and other forms of dementia. The primary endpoint is the percentage change from baseline of CSF cGMP, which is the main PD response to E2027 that may show different responses in subjects with and without amyloid copathology. Further discussion of the selection of the efficacy endpoints is provided in Section 9.2.

Standard safety assessments incorporated into this protocol include assessment of AEs and SAEs, measurement of vital signs, clinical laboratory assessments, physical examinations,

neurologic examinations, ECG measurements, assessments of suicidal thinking and behavior, and UPDRS-III. Safety MRI of the brain may be performed at Unscheduled Visits if deemed appropriate by the investigator.

9.5.4 Reporting of Serious Adverse Events, Pregnancy, and Events Associated with Special Situations

9.5.4.1 Reporting of Serious Adverse Events

All SERIOUS ADVERSE EVENTS, regardless of their relationship to study treatment, must be reported on a completed SAE form by email or fax as soon as possible but no later than 24 hours from the date the investigator becomes aware of the event.

Serious adverse events, regardless of causality assessment, must be collected through the last visit in the Treatment Phase. All SAEs must be followed to resolution or, if resolution is unlikely, to stabilization. Any SAE judged by the investigator to be related to the study treatment or any protocol-required procedure should be reported to the sponsor regardless of the length of time that has passed since study completion.

The detailed contact information for reporting of SAEs is provided in the Investigator Study File.

For urgent safety issues, please ensure all appropriate medical care is administered to the subject and contact the appropriate study team member listed in the Investigator Study File.

It is very important that the SAE report form be filled out as completely as possible at the time of the initial report. This includes the investigator's assessment of causality.

Any relevant follow-up information received on SAEs should be forwarded within 24 hours of its receipt. If the relevant follow-up information changes the investigator's assessment of causality, this should also be noted on the follow-up SAE form.

Preliminary SAE reports should be followed as soon as possible by detailed descriptions including copies of hospital case reports, autopsy reports, and other documents requested by the sponsor.

The investigator must notify his/her IRB/IEC of the occurrence of the SAE in writing, if required by their institution. A copy of this communication must be forwarded to the sponsor or its designee to be filed in the sponsor's Trial Master File.

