9.1.2.2 Follow-Up Period

After the Treatment Period, subjects will complete a Follow-Up Visit 4 weeks after the final dose of study drug. Safety assessments will be completed.

The end of study is defined as the last subject completing the Follow-Up Visit.

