9.5.1.4.1 ADVERSE EVENTS

An AE is any untoward medical occurrence in a patient or clinical investigation subject administered an investigational product. An AE does not necessarily have a causal relationship with the medicinal product. For this study, the study drug is E2027.

The criteria for identifying AEs in this study are:

- Any unfavorable and unintended sign (including an abnormal laboratory finding), symptom, or disease temporally associated with the use of an investigational product, whether or not considered related to the investigational product (Note: Every sign or symptom should not be listed as a separate AE if the applicable disease [diagnosis] is being reported as an AE)

- Any new disease or exacerbation of an existing disease.
- Any deterioration in nonprotocol-required measurements of a laboratory value or other clinical test (eg, ECG or x-ray) that results in symptoms, a change in treatment, or discontinuation of study drug
- Recurrence of an intermittent medical condition (eg, headache) not present pretreatment (Baseline)
- An abnormal laboratory test result should be considered an AE if the identified laboratory abnormality leads to any type of intervention, withdrawal of study drug, or withholding of study drug, whether prescribed in the protocol or not

All AEs, regardless of relationship to study drug or procedure, should be recorded beginning from the time the subject signs the study ICF through the last visit in the Treatment Phase. Refer to Section 9.5.4.1 for the time period after the end of treatment for SAE collection.

Abnormal laboratory values should not be listed as separate AEs if they are considered to be part of the clinical syndrome that is being reported as an AE. It is the responsibility of the investigator to review all laboratory findings in all subjects and determine if they constitute an AE. Medical and scientific judgment should be exercised in deciding whether an isolated laboratory abnormality should be classified as an AE. Any laboratory abnormality considered to constitute an AE should be reported on the Adverse Event eCRF.

Abnormal ECG (QTcF) results, if not otherwise considered part of a clinical symptom that is being reported as an AE, should be considered an AE if the QTcF interval is more than 450 msec and there is an increase of more than 60 msec from baseline. Any ECG abnormality that the investigator considers as an AE should be reported as such.

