AEs that may signal drug abuse potential will require a more detailed follow-up through completion of a specific eCRF form. Similarly, AEs reported during the 28 days following the last dose of study drug (Follow-up Period) that might indicate physical dependency also require a more detailed follow-up through completion of the same eCRF form. This includes AEs that fall into the categories listed below. Examples of such AEs are provided in [Appendix 2](#) and a more comprehensive list is provided in the eCRF Completion Guidelines. This additional follow-up of AEs that signal possible drug abuse potential, including physical dependency following discontinuation of study drug, is in line with current FDA Guidance for Industry for “Assessment for Abuse Potential for Drugs” (FDA 2017 Abuse Potential Guidelines). As neuropsychiatric symptoms are common in DLB, the investigator should exercise clinical judgement in deciding if a neuropsychiatric AE [such as those described in [Appendix 2](#)] constitute an AE of abuse potential.

Euphoria-related terms:

- Euphoric mood
- Elevated mood
- Feeling abnormal
- Feeling drunk
- Feeling of relaxation
- Dizziness
- Thinking abnormal
- Hallucination
- Inappropriate affect

Terms indicative of impaired attention, cognition, and mood:

- Somnolence
- Mood disorders and disturbances

Dissociative/psychotic terms:

- Psychosis
- Aggression

- Confusion and disorientation
- Dissociative state

Related terms not captured elsewhere:

- Drug tolerance
- Habituation
- Substance related disorders

Physical dependence or withdraw (only for events observed within the first 4 weeks after the last dose of study drug):

- Drug withdrawal syndrome

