b: The Screening Period takes place over a period of up to 6 weeks. Subjects who complete screening assessments in less than 6 weeks may proceed to the Baseline Period. At Screening, assessments are grouped into tiers and should be performed sequentially. It is recommended that where appropriate Tiers 1 to 4 should be performed on the same day and Tiers 5 and 6 on a separate day. However, the investigator may perform the various tiers on separate days as appropriate for each subject. Subjects will need to satisfy the eligibility criteria in each tier before proceeding to the next tier. Subjects who cannot complete screening within 6 weeks should be discussed with the sponsor for extension of the Screening Period by up to 1 week.

c: Visit 2 is the Baseline Visit and may be conducted up to 1 week before the first dose of study drug (ie, from Day -7 to Day -1). The Baseline Visit should be at least 2 weeks after the day of Screening Visit Tier 2 assessments and at least 1 week after CSF collection. After completion of study assessments subjects who are eligible will be dispensed with study drug (E2027) before leaving clinic at Visit 2. Visit 3 (Day 1) will be conducted by telephone. On Day 1 the subject will start taking study drug in the morning at home. The site study staff will telephone the subject/caregiver to check that the subject has taken study drug and to elicit information about any AEs. Subjects who develop acute illnesses which make it inappropriate to start taking study drug may have their Baseline Period extended by 1 week after discussion with the sponsor medical monitor.

d: Subjects who discontinue study drug prematurely for any reason will undergo an Early Discontinuation (ED) Visit within 7 days of their final dose of study drug. In addition, subjects who prematurely discontinue study drug are expected to continue in the study for the originally scheduled visits, starting with next such visit that is >7 days after the ED Visit. Subjects who prematurely discontinue the study should attend at least 1 originally scheduled visit after the ED Visit. At these originally scheduled visits that take place after the ED Visit, blood PK samples, plasma biomarker samples, and CSF samples will not be collected.

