5.6.2 Adverse Events

The AE verbatim descriptions (investigator terms from the CRF) will be classified into standardized medical terminology using the MedDRA. Adverse events will be coded to the MedDRA (Version 21.0 or higher) LLT closest to the verbatim term. The linked MedDRA PT and primary SOC will also be captured in the database.

A TEAE is defined as an AE that emerged during treatment or within 28 days following the last dose of study drug, having been absent at pretreatment (Baseline) or

- Reemerged during treatment, having been present at pretreatment (Baseline) but stopped before treatment, or
- Worsened in severity during treatment relative to the pretreatment state, when the AE was continuous.

Only those AEs that are treatment emergent will be included in summary tables. All AEs, treatment emergent or otherwise, will be presented in subject data listings.

Treatment-emergent AEs (TEAEs) will be summarized by subgroup and overall, on the Safety Analysis Set. The incidence of TEAEs will be reported as the number (percentage) of subjects with TEAEs by SOC and PT. A subject will be counted only once within a SOC and PT, even if the subject experienced more than one TEAE within a specific SOC and PT. The number (percentage) of subjects with TEAEs will also be summarized by maximum

severity (mild, moderate, or severe). The number (percentage) of subjects with TEAEs will also be summarized by relationship to study drug (related and not related).

Summaries of common TEAEs will be produced.

A subject data listing of all AEs leading to death will be provided.

The number (percentage) of subjects with treatment-emergent serious adverse events (SAEs) will be summarized by MedDRA SOC and PT for each subgroup and overall. A subject data listing of all SAEs will be provided.

The number (percentage) of subjects with TEAEs leading to discontinuation from study drug will be summarized by MedDRA SOC and PT for each subgroup and overall. A subject data listing of all AEs leading to discontinuation from study drug will be provided.

TEAEs associated with special situations such as overdose, misuse, abuse, medication error, pregnancy, TEAEs with signal of possible drug abuse potential, and those requiring additional Medical Monitor follow-up will be listed and summarized similarly.

A summary of non-treatment emergent AEs will be produced, these are AEs which occurred >28 days after final dose of study drug.

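### AE and SAE collection ends at a visit, while the SAP's treatment-emergent window ends 28 days after the last dose; the two can part for subjects who leave the study or attend Visit 8 early.

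*Protocol*

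**What the plan says.** **Collection.** Protocol 9.5.1.4.1 has all AEs recorded "beginning from the time the subject signs the study ICF through the last visit in the Treatment Phase". Protocol 9.5.4.1 sets the same end for SAEs of any causality: "Serious adverse events, regardless of causality assessment, must be collected through the last visit in the Treatment Phase". It adds an exception: an SAE judged related to treatment or to a protocol-required procedure "should be reported to the sponsor regardless of the length of time that has passed since study completion".

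**Where that end falls.** Protocol 9.1.2 includes the Follow-up Period in the Treatment Phase. Under 9.1.2.2, "subjects will complete a Follow-Up Visit 4 weeks after the final dose". Table 5 puts Visit 7 on Day 84 and Visit 8 on Day 112, and footnote a allows 4 days either way for Visits 4 to 8.

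**Early stopping.** Section 9.3.3 and Table 5 footnote d require an ED Visit within 7 days of the final dose. Subjects who stop drug are expected to keep to the original visits, starting with the next one more than 7 days after the ED Visit. For those who leave the study the request is smaller: "Subjects who prematurely discontinue the study should attend at least 1 originally scheduled visit after the ED Visit". Section 9.5.5 provides for mail or telephone contact, including about AEs, with subjects who cease to return. It gives no duration.

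**Analysis.** SAP 5.6.2 defines a TEAE as one that "emerged during treatment or within 28 days following the last dose of study drug". SAP 8.3.2 ends the safety period 28 days after the last dose. The TEAE definition in protocol 9.7.1.8.2 has no explicit post-dose tail.

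**The concern.** The analysis window is fixed by a dose date and the collection window by a visit date. They coincide only when the last visit falls at least 28 days after the last dose. When it falls earlier, the protocol does not oblige the site to record a new non-serious AE, or an SAE not judged related, that occurs between that visit and day 28. The tables would still describe the window as 28 days.

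The 28-day rule in 9.5.1.4.1 does not close the gap, because it concerns how long AEs are followed rather than how long new ones are sought. That section also sends the reader to 9.5.4.1 for the SAE collection period after treatment, and 9.5.4.1 gives only the visit-based limit.

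AE and SAE incidence is a secondary endpoint, summarised as percentages by subgroup. With 8 treated subjects planned per subgroup, one subject whose event is missed moves that subgroup's incidence by 1/8 = 12.5 percentage points.

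**Working it through.** **Inputs.** Visit days 21, 42, 63, 84 and 112, with a window of ±4 days (Table 5 and footnote a). ED Visit 0 to 7 days after the last dose, and next scheduled visit more than 7 days after the ED Visit (9.3.3, footnote d). Analysis window 28 days (SAP 5.6.2, 8.3.2). Assumptions: a completer's last dose is on the day of Visit 7, and visits after the ED Visit keep their original days.

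**Formula.** Days covered = day of last visit − day of last dose. Days uncollected = max(0, 28 − days covered).

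**The plan's own figure.** On schedule, 112 − 84 = 28 days covered and 0 uncollected. The stated 4 weeks is reproduced.

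**Early Visit 8 (Day 108).**
- Last dose on Day 84: 108 − 84 = 24 covered, 4 uncollected.
- Visit 7 and last dose on Day 88: 108 − 88 = 20 covered, 8 uncollected. This needs both visits at opposite ends of their windows.

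**Stops drug early but stays to Visit 8.** The latest early stop is Day 83.
- Visit 8 on Day 112: at least 112 − 83 = 29 covered, no gap.
- Visit 8 on Day 108: at least 108 − 83 = 25 covered, at most 3 uncollected.

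**Leaves the study after the one requested visit.** The shortest case is an ED Visit on the day of the last dose and a scheduled visit 8 days later, for example last dose and ED Visit on Day 76 and Visit 7 on Day 84. That gives 8 covered and 28 − 8 = 20 uncollected. Enumerating last dose on Days 1 to 83 and ED lag 0 to 7 days, at nominal visit days, gives 83 × 8 = 664 combinations:

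| ED Visit timing | Days from last dose to last visit | Below 28 days |
|---|---|---|
| On day of last dose | 8 to 35 | 73 of 83 |
| 7 days after last dose | 15 to 42 | 45 of 83 |
| All lags 0 to 7 | 8 to 42 (median 22) | 472 of 664 (71%) |

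The mean shortfall over all 664 is 6.7 days.

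**ED Visit only.** 0 to 7 covered, so 21 to 28 uncollected, apart from any contact under 9.5.5. Section 9.3.3 sends subjects who stop drug and study together to end-of-study (Final Visit) procedures, 9.5.5 prescribes the ED procedures, and Table 5 has no column called Final Visit.

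**Follow-up date after early stopping.** Section 9.1.2.2 counts 4 weeks from the final dose, while 9.3.3 and footnote d point to the original schedule, hence Day 112. The first gives a nominal 28 days and the second at least 29. The conflict costs no nominal coverage, but a site cannot tell which date applies. If the visit is anchored to the subject's own final dose, a leaver who attends it loses at most the 4-day window.

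**The case against.** The strongest reply is that collection is in substance tied to the last dose. The Treatment Phase includes the Follow-Up Visit, that visit is set 4 weeks after the final dose, and 9.5.1.4.3 equates the 28 days after the last dose with the Follow-up Period. This stands for subjects on schedule. Those who stop drug but stay to Visit 8 are also covered, to within 3 days.

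Safeguards exist too. Related and procedure-related SAEs are reportable without time limit, so a reader who inferred that SAE collection in general stops early would be wrong. What remains is SAEs not judged related and new non-serious AEs. The mail or telephone contact in 9.5.5 may recover some of these. It applies only to subjects who have ceased to return, and with no stated duration it does not guarantee contact at day 28.

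The ED-only case requires that the further scheduled visit requested in 9.3.3 does not happen. The 8-day completer loss is a double extreme, and a ±4-day window is ordinary. The study is single-arm with descriptive safety summaries, and the SAP's 28 days classifies recorded events without claiming that every event was sought. All of this limits the point's weight but does not make the two windows equal for study leavers.

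**Conclusion.** The point holds in limited form and is minor. On schedule there is no gap. Where the last visit falls short of 28 days after the last dose, collection of new non-serious AEs and SAEs not judged related can miss up to 20 days for a leaver who attends one post-ED visit, and 21 to 28 days if only the ED Visit occurs. An early Visit 8 misses 4 days (at most 8). These figures rest on the two assumptions stated in the working and set aside whatever the 9.5.5 contact recovers.

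A reader might infer three stronger conclusions that the documents do not support:
- That 71% of leavers would be under-observed. The figure is a share of equally weighted scheduling combinations at minimum attendance, not of subjects.
- That 8 of 32 subjects would be affected. The 25% dropout allowance concerns completion of study treatment and does not say how many would leave the study. Eight is an upper guide.
- That events are under-counted in the subjects most likely to have them. Nothing in the documents shows that leavers have more events, and 9.5.5 reports no treatment discontinuations due to adverse events in earlier E2027 studies.

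**What to change.** In protocol 9.5.1.4.1 and 9.5.4.1, extend collection of AEs and any-causality SAEs to the later of the last Treatment Phase visit and 28 days after the last dose. Protocol 9.5.4.2 already uses a similar pairing of last visit and 28 days for pregnancy reports in female subjects. For anyone last seen before day 28, add a telephone contact on or after that day. The protocol already uses telephone AE contact at Visit 3, and this would give the contact in 9.5.5 a time target. For every subject who can still be reached, the uncollected part of the window becomes 0 days.

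Reconcile 9.1.2.2 with 9.3.3 and Table 5 footnote d, so that the follow-up date after early discontinuation is unambiguous.

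The cost is a clause in two sections, a few telephone calls and a few more recorded AEs. No visit or sample is added.
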